#### 2.4.10 Self Administered Health Questionnaires

The Kansas City Cardiomyopathy Questionnaire (KCCQ) helps quantify physical function, symptoms, social function, self-efficacy and knowledge and quality of life. The 36-Item Short Form Health Survey (SF-36) measures physical, mental and general health. The Pulmonary Arterial Hypertension – Symptoms and Impact Questionnaire aims to assess pulmonary hypertension symptoms and their impact on quality of life.

#### 2.5 SPECIMEN COLLECTION AND MANAGEMENT

## 2.5.1 Specimen Handling and Labeling (De-Identification)

Specimens collected will be properly labeled. All research biological specimens and all records associated with the samples will be labeled only with a unique code that contains no personal identifiers. The information linking these code numbers to the corresponding subject's identity will be kept in a secure location in the investigator's office, and will not be available to staff managing samples at the research laboratories.

Sponsor: [name]

Immediately upon receipt of the biological specimens, all attempts will be made to process, isolate, collect, and store the specimens. The code number and date on which the specimen is frozen, all other information about the specimen, and subsequent processing will be entered on the specimen processing worksheet.

## 2.5.2 Specimen Management and Storage

Specimens in excess of immediate assay requirements may be stored indefinitely in a locked freezer under the control of the principal investigator. Subject's de-identified biological samples and data will be stored for future research analyses and may be shared with other researchers', their laboratories or federal repositories. Samples will be sent to the [name] lab at Indiana University, Indianapolis for further analysis. Future sharing outside the institution will be done under an approved data or specimen sharing agreement.

The blood samples will be stored after appropriate coding to remove patient identifiers. The coding information linking patient identifiers to the stored samples will be maintained in a locked, secure area that will be accessible only to the study investigator. Subjects may request to have their samples destroyed at any time. These samples will be destroyed immediately upon receipt of the subjects' written request to do so. Identification of which samples to destroy will be available from the coding information linking patient identifiers to the stored samples as described earlier in this paragraph.

#### 2.5.3 Restrictions to Direct Access of Specimens

Specimens will be kept in the responsible study investigators' laboratories indefinitely and will be under the control of the principal investigator. Investigators or other personnel not involved with the management or operations of the study are not permitted direct access to the specimens.

#### 2.6 ENDPOINTS

## 2.6.1 Primary Endpoints

The primary endpoint of the trial will be mean pulmonary artery pressure (mPAP) during submaximal exercise as compared between placebo and nitrite at 10 weeks (i.e. the week 10 RHC of placebo vs week 10 RHC of nitrite).

#### 2.6.2 Secondary Endpoints

Secondary endpoints:

- 1.The differences in 6MWT with Borg dyspnea scale assessments and pulse oxygen saturation measurements
- 2. RHC hemodynamics (right atrial pressure, pulmonary capillary wedge pressure, pulmonary artery pressures and resistance, pulmonary artery compliance, cardiac output, diastolic pressure gradients, and transpulmonary gradient)
- 3. Doppler-echocardiography
- 4. NT-proBNP plasma levels

- 5. NYHA functional classification changes
- 6. NO2 metabolites
- 7. Endurance exercise time (ET), changes in CPET measurements taken at isotime (oxygen consumption [VO2, L/min], minute ventilation [VE, L/min], ventilatory equivalent [VE/VO2], dead space to tidal volume ratio [Vd/Vt], Borg dyspnea and leg score, and changes in time constants for increases of Vt, respiratory rate [RR], VE, and heartrate).
- 8. Changes in fasting glucose and insulin sensitivity

#### 2.7 SUBJECT WITHDRAWAL

A subject may voluntarily discontinue participation in this study at any time. The investigator may also, at his or her discretion, discontinue a subject from this study at any time. Every effort should be made by the investigator to keep the subject in the study.

Subjects may be withdrawn from the study prior to completion if any of the following criteria are observed:

- Intercurrent illness or an unexpected fatal or life-threatening adverse event, which requires discontinuation of study treatment
- Pregnancy
- Subject reached protocol-defined stopping criteria
- Request by the subject to withdraw from the study
- Protocol violations
- Persistent non-compliance
- Lost to follow-up
- Investigator discretion
- Study closed/terminated

#### 2.7.1. Dropouts and withdrawals

To be considered complete, a subject must complete all study visits as specified in the protocol without violations of the protocol so significant as to obscure the response to study treatment.

Subjects who fail to complete all study required visits will not be considered complete and may not enroll at a later date and will not be replaced. A record will be kept of all subjects who fail to complete all study visits and their primary reasons for discontinuation.

In the event of subject withdrawal, subjects will be encouraged to continue all follow-up visits for safety monitoring or to continue follow up as directed by their personal primary physicians, unless the subject withdraws consent at any time (without having to justify the decision). All available data from subjects who discontinued during the study, for whatever reason, will be included in the safety analysis.

## 2.8 STATISTICAL ANALYSIS

#### 2.8.1 Sample Size and Power

**Sample size:** Prior study has indicated that oral nitrate reduces baseline mean PAP -7 (SD = 4) mm Hg vs. -3 (4) mmHg in placebo group. A sample size of 12 in each group provides 88%

power to detect this difference. This sample size will provide 80% power to detect -10 (6) vs. -5 (6) decrease in post-exercise mPAP in treatment and placebo group, respectively.

**Statistical analysis:** Pre-randomization characteristics of two groups will be presented using the median (interquartile range) or frequency tables at each study sequence. The difference of mPAP during submaximal exercise as compared between placebo and nitrite at 10 weeks (i.e. the week 10 RHC of placebo vs week 10 RHC of nitrite) using the parametric PK-cross analysis (i.e. an ANOVA which determines the sequence, period, carryover, and treatment effects). Post-exercise values of before and after crossover will be compared between two groups using similar approach. For secondary outcomes, we will compare the difference of baseline and follow-up value and compare these differences with a parametric test. Alternatively a nonparametric test will be used for these comparisons. For both primary and secondary outcomes, treatment effect in each sequence as well as mean (SD) total treatment effect and corresponding P values will be reported.

We will also test the effect of treatment on pre-exercise mPAP and secondary outcomes using mixed effect models. In all analysis, missing data will be imputed and sensitivity analysis with imputed data will be performed. All analyses will be performed by ITT approach.

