## Study Aims:

## Specific Aims:

- 1. To evaluate the clinical efficacy and signaling mechanisms of a new FDA-IND approved oral formulation of nitrite (IND# 119526) on exercise tolerance and hemodynamics in PH-HFpEF.
- 2. To monitor *in vivo* formation and metabolism of this new class of signaling electrophile using new FDA IND approved oral nitrite.
- 3. To leverage the methodological tools and insights gleaned over this time to explore fundamental signaling mechanisms of the reactive nitrogen species, nitrite  $(NO_2^-)$ , in the context of pulmonary hypertension (PH) in the setting of the metabolic syndrome.

The study aims to assess the use of oral nitrite vs. placebo on exercise capacity and hemodynamic measurements in subjects with PH-HFpEF.

Subjects will undergo screening procedures to determine that eligibility requirements are met. Prior to receiving the study drug or placebo, subjects will complete baseline assessments.

Subjects (n=26) who meet the inclusion criteria and none of the exclusion criteria will be randomized to study drug (oral nitrite or placebo) for 10 weeks. Subjects will then cross-over to the alternative therapy for an additional 10 weeks and complete all the same testing procedures.

**Drug**: oral formulation of sodium nitrite dose strength in 20 or 40 mg capsules or matching placebo three times daily or TID (once in the morning, in the early afternoon and again in the evening) for the duration of the study.

Subjects will be evaluated as outpatients with the first dose of study drug. Subjects will return at weeks 4 and 8 for safety visits after the start of each study arm. The safety visit will occur to assess adverse events (AE), methemoglobin level, interval histories, brief physical exams, medication compliance review, and dispensing of study drug.

Subjects will also be contacted by the study investigator and/or the study coordinator for a follow-up phone assessment approximately 30 days following the completion of the study.

Planned Sample Size:

26 subjects

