## **Randomization**

Randomization to study drug verses placebo will occur upon completion of all screening and baseline procedures and confirmation by a study physician that subjects have met all eligibility criteria. Randomization of sequence of nitrite-placebo versus placebo-nitrite followed by cross-over to the alternative treatment in a 1:1 ratio according to a computer generated pseudo-random code.

Subjects will self-administer their first dose of study medication or placebo under supervision of the physician investigator or the primary study coordinator after eligibility has been confirmed. Each patient will have their vital signs and methemoglobin measured before taking the study medication and approximately 30-45 minutes after taking their first dose.

Subjects will also be dispensed their study medication for home use including a medication administration diary. Subjects will return the previously dispensed study medication and diary at every study visit thereafter, and medication compliance will be assessed.

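### Section 2.8.1 appears to attach P values to a treatment effect in each sequence, but within one sequence treatment cannot be separated from period

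*Combined protocol and SAP*

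**What the plan says.** The Randomization text under section 2.3.2, repeated in section 2.2.4, sets up a standard AB/BA design: "Randomization of sequence of nitrite-placebo versus placebo-nitrite followed by cross-over to the alternative treatment in a 1:1 ratio". The synopsis plans 26 patients, hence about 13 per sequence.

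Section 2.8.1 analyses the primary endpoint, mPAP during submaximal exercise at week 10 of each treatment, with "an ANOVA which determines the sequence, period, carryover, and treatment effects". On the remaining outcomes it says: "For secondary outcomes, we will compare the difference of baseline and follow-up value", using a parametric or alternatively a nonparametric test. No period term is named in that sentence. A later sentence adds mixed-effect models for pre-exercise mPAP and the secondary outcomes, without listing their terms.

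The reporting rule for all of these outcomes is that "treatment effect in each sequence as well as mean (SD) total treatment effect and corresponding P values will be reported". Nothing in the section calls the by-sequence results descriptive or corrects them for period.

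**The concern.** A by-sequence nitrite minus placebo difference is always also a difference between two periods. If exercise mPAP drifts between the first and second catheterization for any reason, each sequence shows that drift under the label of a treatment effect, with opposite sign in the two sequences.

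Two misreadings could follow. A significant P value from one sequence could be cited as evidence for nitrite when nitrite does nothing. Or a real effect could be dismissed because the two sequences seem to disagree. The rule covers the primary endpoint and all eight groups of secondary endpoints in section 2.6.2, so a report that follows it could hold many such P values.

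**Working it through.** **Inputs from the documents.** 1:1 allocation to two sequences; 26 patients, so 26 / 2 = 13 per sequence; exercise mPAP planned as "80% power to detect -10 (6) vs. -5 (6) decrease in post-exercise mPAP", a difference of 5 mmHg with arm SD 6. Table 1 (section 2.3.6) places exercise catheterization at week 10 and end of treatment only, so there is one exercise value per period and no period baseline.

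**Inputs assumed.** The period shift is not given; 0 to 5 mmHg is shown. The SD of the within-patient difference is not given. With arm SD 6 and within-patient correlation ρ it is 6 × √(2(1 − ρ)), which is 6.00 for ρ = 0.5 and 8.49 for ρ = 0. Alpha is not stated; two-sided 0.05 is used. No carryover is assumed.

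**The plan's own figure.** "A sample size of 12 in each group provides 88"% power for resting mPAP (difference 4 mmHg, SD 4). A paired t-test with n = 12 and difference SD 4 has noncentrality 4 × √12 / 4 = 3.46 on 11 df and gives 88.3%, so the figure is reproduced. The same formula for exercise mPAP (5 × √12 / 6 = 2.89) gives 74.8% against the stated 80%, and no single variant tried reproduces both. The plan therefore does not settle which difference SD applies to exercise mPAP, and a range is needed.

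**What each sequence estimates.** Let τ be nitrite minus placebo and π be period 2 minus period 1.

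- Nitrite-placebo: nitrite falls in period 1, so the difference estimates τ − π.
- Placebo-nitrite: nitrite falls in period 2, so it estimates τ + π.
- Equal-weight average: [(τ − π) + (τ + π)] / 2 = τ. The gap between the two sequences is 2π.

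**False-positive rate when τ = 0.** For a paired t-test within one sequence the noncentrality is π × √13 / SD on 12 df. At π = 3 this is 3 × 3.606 / 6 = 1.80 for SD 6, and 3 × 3.606 / 8.49 = 1.27 for SD 8.49. The chance that at least one of two sequences is significant is 1 − (1 − p)².

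| Shift (mmHg) | One sequence, SD 6 | At least one, SD 6 | One sequence, SD 8.49 | At least one, SD 8.49 |
|---|---|---|---|---|
| 0 | 5.0% | 9.8% | 5.0% | 9.8% |
| 1 | 8.6% | 16.4% | 6.8% | 13.1% |
| 2 | 19.8% | 35.7% | 12.3% | 23.0% |
| 3 | 38.2% | 61.8% | 21.7% | 38.7% |
| 5 | 78.8% | 95.5% | 49.8% | 74.8% |

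The first row is multiplicity alone: 1 − 0.95² = 9.8%. With 12 per sequence and SD 6, the one-sequence rates for 2, 3 and 5 mmHg are 18.4%, 35.3% and 74.8%.

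**When there is a true effect.** With τ = −5 and π = +3 the sequences are expected to show −8 and −2 mmHg. The second is significant in about 20% of trials (SD 6) or 12% (SD 8.49). With τ = −5 and π = +5 they show −10 and 0 mmHg. The average is −5 in both cases. Opposite signs need a shift larger than the treatment effect.

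**The period-adjusted test.** In 40,000 simulated trials per setting (13 per sequence), comparing period differences between the sequences rejected in 4.8% to 5.2% when τ = 0, for shifts of 0, 2, 3 and 5 mmHg. Power for a 5 mmHg effect was about 98% (SD 6) or 82% (SD 8.49), whatever the shift.

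**Secondary outcomes.** Some are measured again at the cross-over visit, for example 6MWT, NT-proBNP and fasting glucose. Change from a period baseline then removes a stable level shift, but not a difference between periods in the amount of change. Section 2.8.1 does not say which baseline serves the second period. Catheterization, echocardiography and IVGTT are not scheduled at that visit.

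**The case against.** The strongest reply is that no decision rests on these figures. The primary comparison is a single nitrite versus placebo contrast, its ANOVA contains period, and no rule in the plan uses a by-sequence result. This stands: a reader might infer that the primary test is invalid, and the documents do not support that.

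The grammar is open too. The P values may belong only to the total effect, in which case the by-sequence effects carry none. This also stands as a possible reading. The plain one covers both, nothing in section 2.8.1 rules it out, and a sentence that allows it needs rewording.

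The size of the problem depends on a shift that the documents do not give. With no shift, each by-sequence test has its nominal 5% error. A period term in the ANOVA allows for a period effect; it does not show that the sponsor expects one.

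A reader might further infer that the total treatment effect is an unadjusted mean of patient differences, and so is biased if the sequences lose unequal numbers. The documents do not say this. The total effect may be the ANOVA estimate, no dropout rate is given, and section 2.8.1 plans imputation and an ITT analysis.

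**Conclusion.** The point holds as a reporting and interpretation problem. If section 2.8.1 is followed on its plain reading, the by-sequence P values test treatment minus or plus period and are not valid tests of treatment. For the primary endpoint nothing measured within a sequence can separate the two.

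The confounding itself is algebra and needs no assumption. Its size does: the rates in the table rest on 13 per sequence, two-sided 0.05, no carryover, and an assumed shift and difference SD. Across shifts of 0 to 5 mmHg, the one-sequence false-positive rate runs from 5% to 79% (SD 6) or from 5% to 50% (SD 8.49). The overall primary test stands. For secondary outcomes with a period baseline the problem is smaller, but it does not vanish.

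**What to change.** Replace the reporting sentence in section 2.8.1 with:

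> For primary and secondary outcomes the treatment effect is the period-adjusted nitrite minus placebo difference from the crossover model, with its 95% CI and P value. Means by sequence and period are listed descriptively, without P values, and are not labelled treatment effects.

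The sentence on testing secondary outcomes, which names no period term, should be brought into line with this.

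The cost is SAP wording. Visits, sample size and data collection do not change. The downside is fewer P values in the report; the means by sequence and period remain available to anyone who wants to see whether the sequences differ.

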#### 3. HUMAN SUBJECTS

#### 3.1 SUBJECT POPULATION

The racial, gender and ethnic characteristics of the proposed subject population in this research protocol shall reflect the demographics of the population of Pittsburgh and the surrounding area. We shall attempt to recruit subjects in proportion to these demographics. No exclusion criteria shall be based on race, ethnicity, or gender.

Every effort will be made to keep subjects in the study until they complete all study procedures.

#### 3.1.1 Inclusion of Women and Minorities

Both men and women of all races and ethnic groups are eligible for this trial. Women who meet the inclusion criteria, and have none of the exclusion criteria, will be enrolled without restriction as dictated by the study protocol. Because of the use of a study medication, woman of child bearing potential must meet specialized inclusion/exclusion criteria to minimize this risk.

#### 3.1.2 Inclusion of Children

Children under the age of 18 will not be recruited for this protocol because of the need to explore potential adverse effects of the study treatment more fully in adults.

#### 3.2 INCLUSION CRITERIA

Potential study subjects must satisfy the following criteria to be enrolled in the study:

- 1. Age 18 years and older
- 2. PH-HFpEF

Confirmed diagnosis by RHC:

- Mean Pulmonary Arterial Pressure (mPAP) ≥ 25 mm Hg AND
- Pulmonary capillary wedge pressure (PCWP) ≥ 15 mm Hg

Page **25** of **47** 

#### AND

- Transpulmonary Gradient (TPG) ≥ 12 mm Hg
- 3. Patient has one or more of the following heart failure associated signs or symptoms: shortness of breath with activity, overweight, atrial fibrillation and/or systemic hypertension.

#### 3.3 EXCLUSION CRITERIA

Subjects meeting any of the exclusion criteria at baseline will be excluded from participating in study.

- Age less than 18 years
- SBP > 170 or < 110 mmHg
- DBP > 95 or < 60 mmHg
- Hemoglobin A1C > 10
- Positive urine pregnancy test or breastfeeding
- Ejection Fraction < 40%
- Dementia
- End-stage malignancy
- Major cardiovascular event or procedure within 6 weeks prior to enrollment
- Severe valvular disease
- Known chronic psychiatric or medical conditions that may increase the risk associated with study participation in the judgement of the investigator would make the subject inappropriate for entry into this study
- Smoker
- Hemoglobin < 9 g/dL
- Serum creatinine > 3.0 mg/dL
- Recent (<3 months) addition or change in dosing of hormonal contraceptive medications (OCP, IUD, DepoProvera)
- Receipt of an investigational product or device, or participation in a drug research study within a period of 15 days;
- RHC < 2 weeks from study screening RHC unless clinically indicated

#### 4. RECRUITMENT AND INFORMED CONSENT PROCEDURES

#### 4.1 RECRUITMENT METHODS

- A variety of mechanisms will be used to recruit subjects for this protocol.
  - a. UPMC

Heart failure patients can be referred by their physician and/or cardiologist from the UPMC Advanced Heart Failure Center, General Cardiology clinic, Benedum Geriatric Center, the Comprehensive Pulmonary Hypertension (PH) Program, internal medicine clinics, or other UPMC or community facilities. For UPMC Presbyterian/Montefiore-based clinics, we will obtain physician and HRPO approval for screening of subject medical records for identification of eligible candidates. He will engage with additional cardiologists, internal medicine physicians, and geriatricians for permission to screen from those clinics. Once identified as preliminarily eligible, the study coordinator/staff will reaffirm with the subject's physician on the clinic visit day that recruitment of the subject is medically appropriate.

Staff will also request direction from the attending physician as to the timing of speaking to the subject, i.e., before or after the subject has seen the physician for their visit. This will be done on a case by case basis. Study staff will speak with candidates at clinic visits or by telephone call to assess interest and review medical history to assess eligibility.

Subjects referred from facilities outside the UPMC Epic medical record system will be provided a medical record release for their cardiologist/physician to release needed documents to confirm eligibility.

Subjects can also be identified from the inpatient Cardiology service. The study coordinator will follow the same procedure as for outpatients by screening the inpatient service for subjects admitted with heart failure symptomatology, check medical history for heart failure diagnoses, and engage the attending cardiologist as to appropriateness for the study. As noted, permission to speak with subject will be obtained from the Cardiology attending.

## b. Research Registry

The HRPO submission will include the request to use the Clinical Translational Science Institute's Pitt+Me Research Registry, which includes a database of over 90,000 individuals who have indicated their interest in participating in research studies. The Pitt+Me initiative includes the use of social media to engage subjects. We will also request to use the University of Pittsburgh's Pepper Center Research Registry which includes a database of older individuals interested in research, fostering inclusion of older adults and covers individuals in the community, assisted living and skilled nursing facilities.

